11.5.3. Physical Examination and Vital Signs

A summary table of Vital Signs parameters described in protocol section 9.4.3.3 will be provided in the TLFs. Descriptive statistics for absolute value and change versus baseline for vital signs (i.e., last assessment prior to dosing) will be presented by time point, treatment and overall.

Investigator judgement (clinically significant/not clinically significant) for vital signs will also be presented by sequence and time point.

Height (in cm), weight (in kg) and BMI calculation (is calculation will be performed in the eCRF) will be analyzed in the baseline table as discussed in section 11.2.

11.5.4. 12-ECG

The 12-lead ECGs will be performed after at least 10-minute rest in supine position, at the time points reported in the study flow chart (section 5.3). The Investigator or a designee will evaluate whether they are normal or abnormal and, if abnormal, whether they are clinically significant. Any occurrence of abnormalities in the cardiac conduction, depolarisation, repolarisation, arrhythmic events and other abnormalities will be evaluated.

The ECG report should be identified with subject details as well as the date and time of recording.

The dated and signed printed version of the ECG will be regarded as source data.

ECGs may be repeated for quality reasons and the results of the repeated ECG will be analysed. Unscheduled ECGs may be collected by the Investigator for safety reasons.

Clinically relevant abnormal findings detected after the signature of the ICF will be reported as AEs in the eCRF.

12-lead ECG parameters will be analyzed on the safety population by means of descriptive tables, similarly to Vital Signs, that will be provided in the TLF. ECG overall investigator judgement will be reported by descriptive statistics by sequence and time point.

11.5.5. Safety laboratory Test

Summary tables of clinical laboratory parameters described in protocol section 9.4.3.4 will be provided in the TLFs.

For biochemistry, haematology, and urinalysis the descriptive statistics and change versus baseline will be reported by analyte, sequence group and time point on the safety population.

For biochemistry, haematology, and urinalysis the Investigator assessment (Normal/ANCS/ACS) frequencies will be reported by analyte, sequence group and time point on the safety population.

For serology the descriptive statistics will be reported by sequence group and overall on the safety population.

For alcohol test, drugs of abuse test and cotinine Test the descriptive statistics will be reported by sequence and overall.

11.5.6. Other Safety variables

Descriptive statistics for absolute value and change of vital signs, 12-lead ECG, physical examination, laboratory tests will be presented by time point, sequence and overall. For these variables, the changes versus baseline (i.e., last assessment prior to dosing) will be presented by time point, sequence and overall.

12.Efficacy evaluations

12.1.Efficacy analysis

N/A

12.2.Subgroup analyses

N/A

12.3 Pharmacokinetic analysis

The PK analysis will be run on the PK population. All PK parameters will be summarised by descriptive statistics as detailed in section 11.2.

Individual concentration versus time profiles (linear and semi-log scales) for Nebivolol,

[figure not shown]
Ramipril and Ramiprilat will be graphically displayed by subject, treatment and period as appropriate. Mean PK concentrations by treatment and period will also be presented using both linear and semi-log scales. For PK parameters C_{max} , $AUC_{(0-t)}$ and $AUC_{(0-\infty)}$, comparative boxplots will be provided for Nebivolol, Ramipril and Ramiprilat by treatment. Box-plots will also be produced for Ramiprilat C_{max} and Ramiprilat and Nebivolol $AUC_{(0-72)}$ by treatment.

12.3.3 Analysis of Primary PK variables

Due to the replicate design adopted for the study, a dedicated approach will be performed to understand whether Ramipril is to be considered an HVD (high variable drug).

First, natural log transformed $AUC_{(0-t)}$ and C_{max} will be analysed using an ANOVA model including sequence, period treatment as fixed effects and subject within sequence as random effect.

After the statistical model has provided the results, the schematic approach below will be followed for Ramipril C_{max} :

After calculating variance of Ramipril C_{max} within Reference Formulation s_{wR}^2 from ANOVA, the coefficient of variation within Reference Formulation CV_{wR} can be calculated with the below formula:

$$CV_{wR} \% = 100 * \sqrt{\exp s_{wR}^2 - 1}$$

If it is true that

$$CV_{wR} > 30\%$$

Then, as EMA's approach suggests, Ramipril will be considered highly variable. Then, s_{wR} will be estimated following this rule:

$$s_{wR} = \begin{cases} \sqrt{s_{wR}^2} & \text{if } 30.00\% < CV_{wR} \leq 50.00\% \\ \sqrt{\ln[0.50^2 + 1]} \approx 0.4724 & \text{if } CV_{wR} > 50\% \end{cases}$$

From the value of s_{wR} it is possible to calculate the limits of the acceptance confidence interval:

$$[L; U] = 100 \exp \{ \mp k * s_{wR} \}$$

where k is the regulatory constant set to $k = 0.760$.

Below it can be seen some examples of how limits of acceptance confidence interval change according to different values of CV_{wR} .

CV_{wR}	Lower Limit L	Upper Limit U
30%	80.00%	125.00%
35%	77.23%	129.48%
40%	74.62%	134.02%
45%	72.15%	138.59%
$\geq 50\%$	69.84%	143.19%

The possibility to widen the acceptance criteria explained above does not apply to the Ramipril $AUC_{(0-t)}$ where the acceptance range should remain at 80.00 – 125.00% regardless of variability.

As anticipated, natural log transformed C_{max} and $AUC_{(0-t)}$ of Nebivolol and Ramipril will be analysed using a mixed effect model including sequence, period and formulation as fixed effects and subject within sequence as random effect.

Estimates of the mean difference (Test formulation – Reference formulation) and corresponding 90% CIs will be obtained from the model for each analyte.

The mean differences and 90% CIs for the differences will be exponentiated to provide estimates of the ratio of geometric means (Test formulation/Reference formulation) and corresponding 90% CIs.

Bioequivalence will be concluded if the 90% CI for the ratio of geometric means for both C_{max} and $AUC_{(0-t)}$ falls wholly within the acceptance range for both Nebivolol and Ramipril. The acceptance range will be 80.00% – 125.00% for all tests except for Ramipril's C_{max} if it will be considered highly variable. In this case, limits of acceptance confidence interval will be calculated as explained above and the bioequivalence will be considered verified if the 90% CI for the GMR of Ramipril's C_{max} falls wholly within the acceptance range and the punctual value of GMR falls within the acceptance range of 80.00% – 125.00%.

Formally, the following Bioequivalence tests will be performed to assess the primary objective:

1. Ramipril of Test formulation versus Ramipril of Reference formulation in term of $AUC_{(0-t)}$
2. Ramipril of Test formulation versus Ramipril of Reference formulation in term of C_{max}
3. Nebivolol of Test formulation versus Nebivolol of Reference formulation in term of $AUC_{(0-t)}$
4. Nebivolol of Test formulation versus Nebivolol of Reference formulation in terms of C_{max} .

For the $AUC_{(0-t)}$ and for Nebivolol's C_{max} , following the $\pm 20\%$ rule, the bioequivalence will be concluded if the mean bioavailability of the test formulation, μ_T , is within $\pm 20\%$ of the mean of the reference formulation, μ_R , i.e., in terms of a ratio of means, if $0.8 < \mu_T / \mu_R < 1.25$. The same limits will be applied if Ramipril won't be considered highly variable, otherwise the limits used for the bioequivalence will be those calculated as explained above. Using the terminology of statistical hypothesis testing, this is accomplished by testing, for each of the eight tests, the hypothesis:

$$H_0: \frac{\mu_T}{\mu_R} \leq L \text{ or } \frac{\mu_T}{\mu_R} \geq U \text{ vs } H_1: L < \frac{\mu_T}{\mu_R} < U$$

Where $L = 0.8$ and $U = 1.25$ for $AUC_{(0-t)}$ of both Nebivolol and Ramipril and Nebivolol's C_{max} , while for C_{max} of Ramipril they will be evaluated.

The SAS syntax used for ANOVA procedure for each of the four tests will be:

```
PROC MIXED DATA=dataset;  
  CLASS formulation subject period sequence;  
  MODEL log(pk variable)= sequence period formulation;  
  RANDOM subject(sequence);  
  ESTIMATE "Test vs Reference" formulation -1 1 / CL ALPHA=0.10;  
  RUN;
```

The SAS syntax used to estimate s_{WR}^2 will be, considering the dataset with only Reference formulation, the following one:

```
PROC GLM DATA = dataset (with only data from Reference formulation)
```

CLASS subject period sequence;

MODEL log (PK variable) = sequence subject(sequence) period;

RUN;

In this way it is possible to obtain in the SAS output the Mean Square Error, so that it can be calculated $CV_{WR}\%$ as explained above.

To reflect the multigroup nature of the study, a sensitivity analysis of the above ANOVA model will be performed after the main bioequivalence analysis including the group effect to the other pre-existing covariates. The term group is based on the day in which the subject was dosed, i.e., all subjects who received their first intake of a study drug on the same day will be assigned to the same group. This sensitivity analysis is useful to understand if the interaction between group and treatment is significant or not. Note that if the groups are not well balanced and not separated in time, statistical analysis using formulation*group term may not be conclusive.

The SAS syntax used for ANOVA procedure including the group effect will be:

PROC MIXED DATA=dataset;

CLASS subject sequence formulation period group;

*MODEL log(pk variable)=group sequence formulation sequence*group period(group)
formulation*group;*

LSMEANS formulation;

*RANDOM subject(sequence*group)*

ESTIMATE "Test vs Reference" formulation -1 1/ CL ALPHA= 0.1;

RUN;

If the formulation*group interaction term is found to be statistically significant and if the size of the groups is considered adequate for inference purposes (i.e., the groups are balanced and greatly separated in time), the primary ANOVA model for assessing the bioequivalence of each analyte will be run within each group.

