10 STATISTICAL METHODS AND DETERMINATION OF SAMPLE SIZE

10.1 Determination of Sample Size

A sample size of 42 subjects (14 subjects per each of the sequences A, B and C) is considered adequate for testing the bioequivalence between NEB/RAM 5/10 mg FDC (Test formulation) and NEB 5mg + RAM 10 mg EC (Reference formulation) at 5% (one side) level of significance with a power higher than 80% based upon a Test versus Reference ratio varying between of 0.95 and 1.05 and an intra-subject coefficient of variation of a maximum of 36.2%.^{(1), (2)} In order to account for approximately a 22% of potential dropouts during the clinical phase and exclusions from the PK population, twelve extra subjects will be included into the study and a total number of 54 subjects will be randomized.

10.2Analysis Populations

Safety population: All subjects receiving at least one administration of study treatment.

*Pharmacokinetic (PK) population*: All subjects who have evaluable and reliable concentrationtime data for deriving the study primary PK parameters for both the Reference and Test formulations and who did not experience major protocol violations or events impacting the PK results.

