- Table 1.13: Descriptive statistics of PK parameters of Nebivolol (after extemporaneous combination intake) by sequence – Analysis Population: PK population
- Table 1.14: Descriptive statistics of PK parameters of Ramipril (after FDC intake) by sequence – Analysis Population: PK population
- Table 1.15: Descriptive statistics of PK parameters of Ramipril (after extemporaneous combination intake) by sequence – Analysis Population: PK population
- Table 1.16: Descriptive statistics of PK parameters of Ramiprilat (after FDC intake) by sequence – Analysis Population: PK population
- Table 1.17: Descriptive statistics of PK parameters of Ramiprilat (after extemporaneous combination intake) by sequence – Analysis Population: PK population
- Table 1.18 Bioequivalence analysis for $AUC_{(0-t)}$, C_{max} and $AUC_{(0-\infty)}$ of Nebivolol including group effect (sensitivity analysis) – Analysis Population: PK population
- Table 1.19: Bioequivalence analysis for $AUC_{(0-t)}$, C_{max} and $AUC_{(0-\infty)}$ of Ramipril including group effect (sensitivity analysis) – Analysis Population: PK population

Safety analysis (safety population)

- Table 2.1.1.1: Overview AEs by Sequence – Analysis Population: Safety
- Table 2.1.1.1: Overview AEs by Treatment – Analysis Population: Safety
- Table 2.1.1: Overview TEAEs by Sequence – Analysis Population: Safety
- Table 2.1.2: Overview ADRs by Sequence – Analysis Population: Safety
- Table 2.2.1: Overview TEAEs by Treatment – Analysis Population: Safety
- Table 2.2.2: Overview ADRs by Treatment – Analysis Population: Safety
- Table 2.3.1: TEAEs by MedRa, SOC and PT by Sequence – Analysis Population: Safety
- Table 2.3.2: ADRs by MedRa, SOC and PT by Sequence – Analysis Population: Safety
- Table 2.3.3: TEAEs by MedRa, SOC and PT by Intensity and Sequence - Analysis Population: Safety
- Table 2.3.4: TEAEs by MedRa, SOC and PT by Causality and Sequence – Analysis Population: Safety
- Table 2.3.5: ADRs by MedRa, SOC and PT by Intensity and Sequence – Analysis Population: Safety
- Table 2.3.6: ADRs by MedRa, SOC and PT by Causality and Sequence – Analysis Population: Safety
- Table 2.4.1: TEAEs by MedRa, SOC and PT by Treatment – Analysis Population: Safety
- Table 2.4.2: ADRs by MedRa, SOC and PT by Treatment – Analysis Population: Safety

-
- Table 2.4.3: TEAEs by MedRa, SOC and PT by Intensity and Treatment – Analysis Population: Safety

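### The group sensitivity model takes its Test/Reference ratio and 90% CI from a fit that keeps formulation*group, so Tables 1.18 and 1.19 could be empty or needlessly imprecise

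*SAP*

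**What the plan says.** SAP 12.3.3 describes a sensitivity analysis to be run after the main bioequivalence analysis. Groups follow the date of first dosing: "all subjects who received their first intake of a study drug on the same day will be assigned to the same group". The SAP gives no expected number of groups, no minimum size and no rule for merging small ones.

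The printed PROC MIXED code has group, sequence, formulation, sequence\*group, period(group) and formulation\*group as fixed effects, with subject nested in sequence\*group as random. The formulation LSMEANS and the ESTIMATE statement with the 90% CI are requested from that same fit, and no coefficients are given for the interaction. The results feed Tables 1.18 and 1.19 in SAP 13.2.1, the first of them described as "of Nebivolol including group effect (sensitivity analysis)".

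The follow-up rule has two conditions. It opens "If the formulation*group interaction term is found to be statistically significant and if the size of the groups is considered adequate for inference purposes", and a parenthesis explains adequacy as balance between groups and wide separation in time. When both conditions hold, "the primary ANOVA model for assessing the bioequivalence of each analyte will be run within each group". The SAP also warns that the interaction analysis may be inconclusive for unbalanced groups that are close in time.

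Two other passages matter. SAP section 8 says that a subject who does not complete the three sessions is replaced by a new subject in the same sequence. The bioequivalence decision rule earlier in 12.3.3 rests on the model without group.

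**The concern.** A model with formulation\*group is the right one for testing whether the formulation difference varies between cohorts. It is a poor one for an overall formulation difference. Once the interaction is in, the overall contrast is an average of group-specific differences, so every group must be able to supply its own difference, and the average needs weights. The SAP settles neither point, and grouping by dosing day can produce very small groups.

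At stake is whether the sensitivity tables can be used. A sensitivity analysis for group should show whether allowing for cohorts changes the primary ratio. This one can return no ratio at all, or a wider interval caused only by the weighting, which could be misread as the primary result not being robust.

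**Working it through.** **Inputs.** Protocol 10.1: 42 evaluable subjects (14 per sequence), 54 randomised, one-sided 5%, "a Test versus Reference ratio varying between of 0.95 and 1.05", and "an intra-subject coefficient of variation of a maximum of 36.2" per cent. Protocol 10.3.3: limits 80.00–125.00%. Protocol Table 1: sequences TRR (A), RRT (B) and RTR (C). Group sizes are not in the documents; those below are assumptions. Sequences are taken as balanced within groups except where stated.

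**1. The plan's own figure.** The within-subject log variance is s² = ln(1 + 0.362²) = 0.1231, so s = 0.351. For this partial replicate the variance of the Test–Reference difference is 1.5·s²/n, with 2n − 3 degrees of freedom. At n = 42 the SE is √(1.5 × 0.1231/42) = 0.0663 with 81 df. Two one-sided tests then have 81.5% power at ratio 0.95 and 82.4% at 1.05, and 42/(1 − 0.22) = 53.8 rounds up to 54. The stated figures reproduce.

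**2. Is the overall contrast estimable?** In a group where everyone has the same sequence, Test always falls in the same period. The Test column for that group is then identical to one period(group) column, so that group has no formulation difference of its own and no average over groups can include it. A rank check of the fixed-effect design gives:

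| Groups | With formulation\*group, equal coefficients | Without formulation\*group |
|---|---|---|
| 21 / 21 | estimable | estimable |
| 36 / 6 | estimable | estimable |
| 21 / 21 / 1 | not estimable | estimable |
| 27 / 2, the two in one sequence | not estimable | estimable |
| 27 / 2, the two in different sequences | estimable | estimable |

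If the interaction coefficients are read literally as zero, the contrast is not estimable in any of these layouts with the interaction in the model. The table assumes the usual software behaviour of spreading them equally over groups.

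**3. Cost of equal weights when the contrast is estimable.** With G groups of size n_g and total N, the variance is (1.5·s²/G²)·Σ(1/n_g), against 1.5·s²/N without the interaction. Ignoring the small change in degrees of freedom, the CI width ratio on the log scale is √(N·Σ(1/n_g)/G²).

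- 21/21: √(42 × (1/21 + 1/21)/4) = 1.00
- 30/12: √(42 × (1/30 + 1/12)/4) = √1.225 = 1.11
- 42/12 (all 54 evaluable): √(54 × (1/42 + 1/12)/4) = √1.446 = 1.20
- 36/6: √(42 × (1/36 + 1/6)/4) = √2.042 = 1.43

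At CV 36.2%, ratio 0.95 and 42 evaluable subjects, the chance that the sensitivity CI lies inside 80–125% is 81.5% for 21/21, 73.1% for 30/12 and 45.1% for 36/6. Without formulation\*group (df = 2N − 2G − 1 = 79 for two groups) it is 81.5% in all three layouts.

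**4. Power of a within-group run.** For a balanced group of 21 the variance is 1.5·s²/21 with 39 df. Power at ratio 0.95 with 80–125% limits is 45% at CV 36.2% and 81% at CV 25%.

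**The case against.** The case for leaving the SAP alone has real substance. The model's stated purpose is to learn whether formulation and group interact, and that survives a singleton group: in the 21/21/1 layout one interaction degree of freedom can still be tested. The SAP itself warns about unbalanced groups. The group sizes used above are assumed, and the SAP does not say that replacements will be dosed alone. All of this stands. It does not explain why the ratio and CI are taken from this model, and the SAP's warning concerns the interaction analysis, not a missing or reweighted ratio.

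Three stronger readings are tempting and are not supported.

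- A reader might infer that a chance-significant interaction alone sets off within-group bioequivalence runs. The SAP also requires balanced groups well separated in time. Over four independent tests at an assumed 5%, the chance of at least one false interaction would be 1 − 0.95⁴ = 18.5%. That is not the chance of triggering the runs: it ignores the second condition, Cmax and AUC come from the same profiles, and the SAP states no level.
- A reader might infer that within-group results could displace the pooled conclusion. SAP 12.3.3 places the decision with the model without group, SAP 13.2.1 lists no within-group bioequivalence table, and Protocol 10.5 requires a substantial amendment to change the primary analysis. Only an explicit sentence on discordant results is missing.
- A reader might infer that imprecise weighting and underpowered within-group runs compound each other. They mostly exclude each other: weighting costs precision in unequal groups, while the runs are allowed only in balanced ones, where equal weighting costs little or nothing.

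The 45% figure is also a worst case. It uses the planning maximum CV and unwidened limits; ramipril Cmax at that CV would have wider limits, giving about 68% for a group of 21.

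**Conclusion.** The point holds for the sensitivity estimate and CI. With formulation\*group kept in the model, Tables 1.18 and 1.19 would have no ratio if any dosing-day group contained only one sequence. With unequal groups they would show a CI wider than the data require: 1.11 to 1.43 times in the layouts examined, and no wider for equal groups. This rests on two assumptions outside the documents: the group sizes, and the equal spreading of interaction coefficients. The primary conclusion and its type I error are untouched. The missing interaction level and the status of within-group results are secondary clarifications.

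**What to change.** In SAP 12.3.3:

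1. Use the model with formulation\*group only for the interaction p-value, at a stated level.
2. Take the sensitivity ratio and 90% CI for Tables 1.18 and 1.19 from the model with group, sequence, sequence\*group, period(group) and formulation, without formulation\*group.
3. For the interaction test, merge a dosing day with the adjacent cohort only if all its subjects are in one sequence. Two different sequences are enough for estimability, so a wider merging rule is not needed.
4. State that within-group runs, if both conditions are met, are descriptive and that the pooled primary model decides bioequivalence.

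The cost is one additional model statement and a few sentences, with no change to sample size or conduct. The downside is that no formal bioequivalence claim can be made for a single group; at the planning CV, groups of about 21 could not reliably support one.

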12.3.4 Analysis of secondary PK variables

- The following secondary PK variables for the analytes Nebivolol and Ramipril will be compared when administered as FDC tablet vs. EC:
 - $AUC_{(0-\infty)}$ will be analysed similarly to $AUC_{(0-t)}$.
 - Other PK parameters will be summarized descriptively.

12.3.5 Analysis of exploratory PK variables

Exploratory PK parameters will be summarised descriptively. The bioequivalence testing may also be conducted for Ramiprilat in case of inconclusive results for the BE based on Ramipril.

13. Tables, listings and figures

13.1. Statistical Analysis Report

The TLF (Tables, Listings and Figures) will follow the list of tables, plots, and listings agreed with the other teams involved in the study conduction.

13.2. Index of TLFs

13.2.1 Tables

Subject Disposition

- Table 1.1: Overall subject disposition by sequence
- Table 1.2: Presence of subjects at study visits by sequence – Analysis Population: Safety

Demographics and baseline characteristics

- Table 2.1: Demographics and baseline characteristics by sequence – Analysis Population: Safety
- Table 2.2: Demographics and baseline characteristics by sequence – Analysis Population: PK
- Table 2.3: Demographics characteristics by gender – Analysis Population: PK
- Table 2.4: Pregnancy test by time point and sequence - Analysis Population: Safety

Pharmacokinetic analysis (PK population)

- Table 1.1: Bioequivalence analysis for $AUC_{(0-t)}$, C_{max} and $AUC_{(0-\infty)}$ of Nebivolol – Analysis Population: PK population
- Table 1.2: Bioequivalence analysis for $AUC_{(0-t)}$, C_{max} and $AUC_{(0-\infty)}$ of Ramipril – Analysis Population: PK population
- Table 1.3: Descriptive statistics of Nebivolol PK parameters by treatment and period – Analysis Population: PK population
- Table 1.4: Descriptive statistics of Ramipril PK parameters by treatment and period – Analysis Population: PK population
- Table 1.5: Descriptive statistics of Ramiprilat PK parameters by treatment and period – Analysis Population: PK population
- Table 1.6: Descriptive statistics of Plasma Concentrations of Nebivolol (after FDC intake) by sequence and time point – Analysis Population: PK population
- Table 1.7: Descriptive statistics of Plasma Concentrations of Nebivolol (after extemporaneous combination intake) by sequence and time point – Analysis Population: PK population
- Table 1.8: Descriptive statistics of Plasma Concentrations of Ramipril (after FDC intake) by sequence and time point – Analysis Population: PK population

- Table 1.9: Descriptive statistics of Plasma Concentrations of Ramipril (after extemporaneous combination intake) by sequence and time point – Analysis Population: PK population
- Table 1.10: Descriptive statistics of Plasma Concentrations of Ramiprilat (after FDC intake) by sequence and time point – Analysis Population: PK population
- Table 1.11: Descriptive statistics of Plasma Concentrations of Ramiprilat (after extemporaneous combination intake) by sequence and time point – Analysis Population: PK population
- Table 1.12: Descriptive statistics of PK parameters of Nebivolol (after FDC intake) by sequence – Analysis Population: PK population
- Table 1.13: Descriptive statistics of PK parameters of Nebivolol (after extemporaneous combination intake) by sequence – Analysis Population: PK population
- Table 1.14: Descriptive statistics of PK parameters of Ramipril (after FDC intake) by sequence – Analysis Population: PK population
- Table 1.15: Descriptive statistics of PK parameters of Ramipril (after extemporaneous combination intake) by sequence – Analysis Population: PK population
- Table 1.16: Descriptive statistics of PK parameters of Ramiprilat (after FDC intake) by sequence – Analysis Population: PK population
- Table 1.17: Descriptive statistics of PK parameters of Ramiprilat (after extemporaneous combination intake) by sequence – Analysis Population: PK population
- Table 1.18 Bioequivalence analysis for $AUC_{(0-t)}$, C_{max} and $AUC_{(0-\infty)}$ of Nebivolol including group effect (sensitivity analysis) – Analysis Population: PK population
- Table 1.19: Bioequivalence analysis for $AUC_{(0-t)}$, C_{max} and $AUC_{(0-\infty)}$ of Ramipril including group effect (sensitivity analysis) – Analysis Population: PK population

Safety analysis (safety population)

- Table 2.1.1.1: Overview AEs by Sequence – Analysis Population: Safety
- Table 2.1.1.1: Overview AEs by Treatment – Analysis Population: Safety
- Table 2.1.1: Overview TEAEs by Sequence – Analysis Population: Safety
- Table 2.1.2: Overview ADRs by Sequence – Analysis Population: Safety
- Table 2.2.1: Overview TEAEs by Treatment – Analysis Population: Safety
- Table 2.2.2: Overview ADRs by Treatment – Analysis Population: Safety
- Table 2.3.1: TEAEs by MedRa, SOC and PT by Sequence – Analysis Population: Safety
- Table 2.3.2: ADRs by MedRa, SOC and PT by Sequence – Analysis Population: Safety
- Table 2.3.3: TEAEs by MedRa, SOC and PT by Intensity and Sequence - Analysis Population: Safety
- Table 2.3.4: TEAEs by MedRa, SOC and PT by Causality and Sequence – Analysis Population: Safety
- Table 2.3.5: ADRs by MedRa, SOC and PT by Intensity and Sequence – Analysis Population: Safety
- Table 2.3.6: ADRs by MedRa, SOC and PT by Causality and Sequence – Analysis Population: Safety
- Table 2.4.1: TEAEs by MedRa, SOC and PT by Treatment – Analysis Population: Safety
- Table 2.4.2: ADRs by MedRa, SOC and PT by Treatment – Analysis Population: Safety

-
- Table 2.4.3: TEAEs by MedRa, SOC and PT by Intensity and Treatment – Analysis Population: Safety
 - Table 2.4.4: TEAEs by MedRa, SOC and PT by Causality and Treatment – Analysis Population: Safety
 - Table 2.4.5: ADRs by MedRa, SOC and PT by Intensity and Treatment – Analysis Population: Safety
 - Table 2.4.6: ADRs by MedRa, SOC and PT by Causality and Treatment – Analysis Population: Safety
 - Table 2.5: Haematology by sequence and Visit and their change versus baseline – Analysis Population: Safety
 - Table 2.6: Biochemistry by sequence and Visit and their change versus baseline – Analysis Population: Safety
 - Table 2.7: Urinalysis by sequence and Visit and their change versus baseline – Analysis Population: Safety
 - Table 2.8: Vital signs by sequence and Time Point and their change versus baseline – Analysis Population: Safety
 - Table 2.9: ECG by sequence and Time Point and their change versus baseline – Analysis Population: Safety
 - Table 2.10: Haematology Investigator Judgment by Sequence and visit – Analysis Population: Safety
 - Table 2.11: Biochemistry Investigator Judgment by Sequence and visit – Analysis Population: Safety
 - Table 2.12: Urinalysis Investigator Judgment by Sequence and visit – Analysis Population: Safety
 - Table 2.13: ECG Investigator Judgment by Sequence and time point – Analysis Population: Safety
 - Table 2.14: Vital signs Investigator Judgment by Sequence and time point – Analysis Population: Safety
 - Table 2.15: Serology by sequence (HIV-1, HIV-2, hepatitis B, hepatitis C and SARS-CoV-2) – Analysis Population: Safety
 - Table 2.16: Toxicology: Alcohol breath test, drugs abuse and Cotinine Test by sequence – Analysis Population: Safety

